10.6 Clinical Study Termination

The Study Sponsor reserves the right to close the investigational site or terminate the study in its entirety at any time.

If the clinical study is prematurely terminated or suspended by the Study Sponsor:

- The Study Sponsor must:
 - Immediately notify the Investigator(s) and subsequently provide instructions for study termination.
 - Inform the Investigator and the regulatory authorities of the termination/suspension and the reason(s) for the termination/suspension.
- The Investigator must:
 - Promptly notify the IRB/IEC of the termination or suspension and of the reasons.
 - Provide subjects with recommendations for post-study treatment options as needed.

The Investigator may terminate the site's participation in the study for reasonable cause.

10.6.1 Follow-up of subjects after study participation has ended

Following this study, the subject will return to their eye care professional for their routine eye care.

11 ADVERSE EVENTS AND DEVICE DEFICIENCIES

11.1 General Information

An AE is any untoward medical occurrence, unintended disease or injury, or untoward clinical signs (including abnormal laboratory findings) in subjects, users, or other persons, whether or not related to the investigational medical device (test article). Refer to the Glossary of Terms and figures below for categories of AEs and SAEs.

Figure 11-1 Categorization of All AEs

[figure not shown]
[figure not shown]

Figure 11-2 Categorization of All SAE

SAEs

In addition to reporting all AEs (serious and non-serious) meeting the definitions, the Investigator must report any occurrence of the following as an SAE:

- An ocular infection including a presumed infectious ulcer with any of the following characteristics*:
 - Central or paracentral location
 - Penetration of Bowman's membrane
 - Infiltrates > 2 mm diameter
 - Iritis
 - Increase in intraocular pressure
 - Culture positive for microorganisms
 - Increasing size or severity at subsequent visits
- Any central or paracentral corneal event (such as neovascularization) that results in permanent opacification

- Hypopyon
- Hyphema
- Neovascularization within the central 6 mm of the cornea
- Permanent vision loss as defined by loss of 2 or more lines of BCVA from enrollment visit that fails to resolve
- Uveitis (anterior, intermediate, or posterior)
- Corneal abrasion affecting \geq 50% of corneal surface area

Significant Non-Serious AE

A significant non-serious AE is a device-related, non-sight threatening AE that warrants discontinuation of any contact lens wear for greater than or equal to 2 weeks. In addition, the Investigator must report any occurrence of the following as a Significant Non-Serious Adverse Event:

- Peripheral non-progressive non-infectious ulcers
- All symptomatic corneal infiltrative events
- Corneal staining score greater than or equal to Grade 3
- Temporary vision loss as defined by loss of 2 or more lines of BCVA from enrollment visit that persists for 2 or more weeks
- Neovascularization score greater than or equal to Grade 2

Device Deficiencies

A device deficiency is inadequacy of a medical device with respect to its identity, quality, durability, reliability, safety, or performance. A device deficiency may or may not be associated with subject harm (ie, ADE or SADE); however, not all ADEs or SADEs are due

to a device deficiency. The Investigator should determine the applicable category listed in the Device Deficiency eCRF for the identified or suspect device deficiency and report any subject harm separately. Examples of device deficiencies include the following:

- Failure to meet product specifications (eg, incorrect lens power/diameter/base curve/color)
- Lens cloudy
- Lens surface/edge defect
- Torn lens during handling/in pack
- Packaging deficit (eg, mislabeled product)
- Suspect product contamination
- Lack of performance

11.2 Monitoring for AEs

At each visit, after the subject has had the opportunity to spontaneously mention any problems, the Investigator should inquire about AEs by asking the standard questions:

- “Have you had any health problems since your last study visit?”
- “Have there been any changes in the medicines you take since your last study visit?”

[figure not shown]

11.3 Procedures for Recording and Reporting

AEs are collected from the time of informed consent. Any pre-existing medical conditions or signs/symptoms present in a subject prior to the start of the study (ie, before informed consent is signed) are not considered AEs in the study and should be recorded in the Medical History section of the eCRF.

- ADEs or SAEs are documented on the *Serious Adverse Event and Adverse Device Effect* eCRF within 24 hours of the Investigator's or site's awareness.
- Device deficiencies are documented on the *Device Deficiency* eCRF within 24 hours of the Investigator's or site's awareness.
- A printed copy of the completed *Serious Adverse Event and Adverse Device Effect* and/or *Device Deficiency* eCRF must be included with product returns.
- Additional relevant information after initial reporting must be entered into the eCRF as soon as the data become available.
- Document any changes to concomitant medications on the appropriate eCRFs.
- Document all relevant information from Discharge Summary, Autopsy Report, Certificate of Death, etc, if applicable, in narrative section of the *Serious Adverse Event and Adverse Device Effect* eCRF.

Intensity and Causality Assessments

Where appropriate, the Investigator must assess the intensity (severity) of the AE based upon medical judgment with consideration of any subjective symptom(s), as defined below:

Intensity (Severity)

Mild An AE is mild if the subject is aware of but can easily tolerate the sign or symptom.

Moderate An AE is moderate if the sign or symptom results in discomfort significant enough to cause interference with the subject's usual activities.

[figure not shown]
Severe An AE is severe if the sign or symptom is incapacitating and results in the subject's inability to work or engage in their usual activities.

For every AE in the study, the Investigator must assess the causality (Related or Not Related to the medical device or study procedure). An assessment of causality will also be performed by Study Sponsor utilizing the same definitions, as shown below:

Causality

Related An AE classified as related may be either definitely related or possibly related where a direct cause and effect relationship with the medical device or study procedure has not been demonstrated, but there is a reasonable possibility that the AE was caused by the medical device or study procedure.

Not Related An AE classified as not related may either be definitely unrelated or simply unlikely to be related (ie, there are other more likely causes for the AE).

11.5 Unmasking of the Study Treatment

Masked information on the identity of the assigned medical device should not be disclosed during the study. [REDACTED]

[REDACTED]

[REDACTED]

[REDACTED]

[REDACTED]

[REDACTED]

11.6 Follow-Up of Subjects with AEs

The Investigator is responsible for adequate and safe medical care of subjects during the study and for ensuring that appropriate medical care and relevant follow-up procedures are maintained after the study.

[REDACTED]

11.7 Pregnancy in the Clinical Study

Women of childbearing potential or women who are pregnant at the time of study entry are not excluded from participation. [REDACTED]

[REDACTED]

[REDACTED]

[REDACTED]

12 ANALYSIS PLAN

Any deviations to the analysis plan will be updated during the course of the study as part of a protocol amendment or will be detailed in the clinical study report.

All analyses will be conducted according to the applicable statistical analysis plan.

12.1 Subject Evaluability

Final subject evaluability must be determined prior to breaking the code for masked treatment (lens) assignment and locking the database, based upon the Deviations and Evaluability Plan.

12.2 Analysis Sets

Five analysis sets will be defined:

- a) All Enrolled – all subjects signing the informed consent form
- b) Enrolled Dispensed – subjects/eyes from All Enrolled that have been exposed to study lenses [REDACTED]
- c) Enrolled Not Dispensed – subjects/eyes from All Enrolled that have not been exposed to study lenses [REDACTED]
- d) Completed – Enrolled Dispensed subjects/eyes completing the study
- e) Discontinued – Enrolled Dispensed subjects/eyes not complete the study

12.3 Demographic and Baseline Characteristics

Demographic information, [REDACTED] will be presented by lens group and overall [REDACTED]
[REDACTED]
[REDACTED]

12.4 Effectiveness Analyses

For [REDACTED] the primary [REDACTED], separate summary tables will be prepared, when applicable, for the Completed and the Discontinued analysis sets as follows:

- Completed Control (eyes/subjects)
- Completed Test (eyes/subjects)

- Discontinued Control (eyes/subjects)
- Discontinued Test (eyes/subjects)

No inferential testing will be performed on effectiveness endpoints,

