	
■ [REDACTED]
 
Safety
 
 • AEs • Biomicroscopy • Device deficiencies
Study Design	
This will be a prospective, randomized, [REDACTED] controlled, double-masked, parallel-group, daily wear clinical study. Subject participation in the study will be approximately 14 weeks with approximately 3 months of exposure to study lenses.

Subject population	
Volunteer subjects aged 18 or over who are adapted daily wear frequent replacement soft contact lens wearers, excluding Biofinity habitual wearers, have at least 3 months of soft contact lens wearing experience, and who wear their habitual lenses at least 5 days per week and at least 8 hours per day.
 
[REDACTED]
 
[REDACTED]
 
[REDACTED]
 
[REDACTED]
 
[REDACTED]

Key inclusion criteria (See Section 8.1 for a	
 • Successful wear of spherical daily wear frequent replacement soft contact lenses for distance correction in both eyes during the past 3 months for a minimum of 5 days per week and 8 hours per day.

complete list of inclusion criteria)	
 Manifest cylinder \leq 0.75 D in each eye
Key exclusion criteria (See Section 8.2 for a complete list of exclusion criteria)	
 Wearing habitual contact lenses in an extended wear modality (routinely sleeping in lenses for at least 1 night per week) over the last 3 months prior to enrollment. Monovision contact lens wearers Habitually wearing Biofinity lenses
Data analysis and sample size justification	
[REDACTED]
 
[REDACTED]
 
effectiveness and safety data will be presented separately based upon subject study status of Completed or Discontinued.
 
No formal hypotheses are formulated for the primary effectiveness endpoint, hence no inferential testing will be performed.
 
[REDACTED]
 
[REDACTED]
 
[REDACTED]
 
[REDACTED]
 
[REDACTED]
 
[REDACTED]

Key words	[REDACTED] Biofinity, daily wear, [REDACTED]
Associated materials	
CLEAR CARE Cleaning & Disinfecting Solution will be used for daily cleaning and disinfection.
 
[REDACTED]
 
[REDACTED]
 
[REDACTED]
 
[REDACTED]

Table 3-1 Schedule of Study Procedures and Assessments

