12.4.1 Analysis of Primary Effectiveness Endpoint(s)

[figure not shown]
The primary objective of this study is to demonstrate safety and effectiveness of [REDACTED] soft contact lens when worn for daily wear as compared to Biofinity soft contact lens.

The primary effectiveness endpoint is distance VA with study lenses, collected in Snellen, for each eye. Conversion will be made to the logMAR scale.

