12.5 Handling of Missing Data

All data obtained in evaluable subjects/eyes will be used. No imputation for missing values will be carried out.

Incidence and reasons for discontinuation by lens group will be tabulated at each visit and overall.

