1.1 Study Objectives

PRIMARY OBJECTIVE

The primary objective is to demonstrate safety and effectiveness of [REDACTED] soft contact lens when worn for daily wear as compared to Biofinity soft contact lens.

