1.2 Study Description

Key components of the study are summarized in Table 1-1.

Table 1-1 Study Description Summary

[figure not shown]
Study Design	Prospective, multi-center, randomized, [REDACTED] controlled, double-masked, parallel-group
Study Population	Volunteer subjects aged 18 or over who are adapted daily wear frequent replacement soft contact lens wearers, excluding Biofinity habitual wearers, have at least 3 months of soft contact lens wearing experience, and who wear their habitual lenses at least 5 days per week and at least 8 hours per day. [REDACTED] [REDACTED] [REDACTED] [REDACTED] [REDACTED] Target to complete: 90 subjects (60:30; Test:Control) Planned to enroll: ~120 subjects
Number of Sites	~8 (US)
Test Product	[REDACTED] soft contact lenses [REDACTED]
Control Product	CooperVision® BIOFINITY® (comfilcon A) soft contact lenses (Biofinity)
Duration of Treatment	Approximately 3 months
Visits	Visit 1: Screening/Baseline/Dispense (Day 1) Visit 2: Week 1 Follow-up Visit 3: Week 2 Follow-up Visit 4: Month 1 Follow-up Visit 5: Month 2 Follow-up Visit 6: Month 3 Follow-up/Exit

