2.5 Discontinued

The Discontinued analysis set consists of Enrolled Dispensed subjects/eyes not completing the study.

3 Subject Characteristics and Study Conduct Summaries

Demographic information (age, sex, ethnicity, and race), recent lens wearing experience (wear modality, wear success), and habitual lens information will be presented by lens group and overall [REDACTED]

[REDACTED].

[REDACTED]

[REDACTED]
[REDACTED]
[REDACTED]
[REDACTED]
[REDACTED]
[REDACTED]

4 Effectiveness Analysis Strategy

This study defines one primary effectiveness endpoint [REDACTED]

[REDACTED]. Unless otherwise specified, separate summary tables will be presented for the Completed and the Discontinued analysis sets with the following distinction:

- Completed Control (eyes/subjects)
- Completed Test (eyes/subjects)

- Discontinued Control (eyes/subjects)
- Discontinued Test (eyes/subjects)

No inferential testing will be performed on the effectiveness endpoints,

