5.3.3 Device Deficiencies

A frequency table showing counts for each treatment-emergent Device Deficiency category will be presented. In addition, listings for treatment-emergent and pre-treatment device deficiencies will be provided.

8 References

9 Revision History

This is the original (Version 1.0) Statistical Analysis Plan for this study. This version of the Statistical Analysis Plan is based on Version 1.0 of the study protocol.

10 Appendix

Table 10-1 Schedule of Study Procedures and Assessments

Procedure/ Assessment	Visit 1 Screening/ Baseline/ Dispense	Visit 2 Week 1 Follow-up	Visit 3 Week 2 Follow-up	Visit 4 Month 1 Follow-up	Visit 5 Month 2 Follow-up	Visit 6 Month 3 Follow-up/Exit	Early Exit	USV
	Day 1	Day 7	Day 15	Day 30	Day 60	Day 95		
Informed Consent	✓	-	-	-	-	-	-	-
Demographics	✓	-	-	-	-	-	-	-
Medical History	✓	✓	✓	✓	✓	✓	✓	(✓)
Concomitant Medications	✓	✓	✓	✓	✓	✓	✓	(✓)
Inclusion/ Exclusion	✓	-	-	-	-	-	-	-
Habitual lens information (brand / manufacturer, modality, power, wear success, habitual lens care brand)	✓	-	-	-	-	-	-	-
VA w/ habitual correction (OD,OS Snellen distance)	✓	-	-	-	-	✓	✓	(✓)
██████████	████	████	████	████	████	████	████	████

Procedure/ Assessment	Visit 1 Screening/ Baseline/ Dispense	Visit 2 Week 1 Follow-up	Visit 3 Week 2 Follow-up	Visit 4 Month 1 Follow-up	Visit 5 Month 2 Follow-up	Visit 6 Month 3 Follow-up/Exit	Early Exit	USV
	Day 1	Day 7	Day 15	Day 30	Day 60	Day 95		
[REDACTED]	[REDACTED]	[REDACTED]	[REDACTED]	[REDACTED]	[REDACTED]	[REDACTED]	[REDACTED]	[REDACTED]
[REDACTED]	[REDACTED]	[REDACTED]	[REDACTED]	[REDACTED]	[REDACTED]	[REDACTED]	[REDACTED]	[REDACTED]
Biomicroscopy	✓	✓	✓	✓	✓	✓	✓	(✓)
[REDACTED]	[REDACTED]	[REDACTED]	[REDACTED]	[REDACTED]	[REDACTED]	[REDACTED]	[REDACTED]	[REDACTED]
Randomize	✓	-	-	-	-	-	-	-
[REDACTED]	[REDACTED]	[REDACTED]	[REDACTED]	[REDACTED]	[REDACTED]	[REDACTED]	[REDACTED]	[REDACTED]
IP Dispense	✓	✓	(✓)	(✓)	(✓)	-	-	(✓)
VA w/ study lenses (OD, OS Snellen distance) ¹	✓	✓	✓	✓	✓	✓	✓	(✓)
[REDACTED]	[REDACTED]	[REDACTED]	[REDACTED]	[REDACTED]	[REDACTED]	[REDACTED]	[REDACTED]	[REDACTED]

Procedure/ Assessment	Visit 1 Screening/ Baseline/ Dispense	Visit 2 Week 1 Follow-up	Visit 3 Week 2 Follow-up	Visit 4 Month 1 Follow-up	Visit 5 Month 2 Follow-up	Visit 6 Month 3 Follow-up/Exit	Early Exit	USV
	Day 1	Day 7	Day 15	Day 30	Day 60	Day 95		
[REDACTED]								

Printed By:

Print Date:

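### In the readable text, visual acuity with study lenses is compared by lens only within Completed and within Discontinued wearers; a by-lens summary of all dispensed wearers should be added

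*Protocol*

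**What the plan says.** - **Objective.** SAP 1.1 sets out to show safety and effectiveness of the test "soft contact lens when worn for daily wear as compared to Biofinity soft contact lens". Protocol 9.3 and SAP 1.3 randomise 2:1.
- **Endpoint.** Protocol 12.4.1: "The primary effectiveness endpoint is distance VA with study lenses, collected in Snellen, for each eye". Values are converted to logMAR, and SAP 4.3.1 provides summary statistics at each visit. Neither document plans a test.
- **Tables.** Protocol 12.4: "separate summary tables will be prepared, when applicable, for the Completed and the Discontinued analysis sets as follows", followed by Control and Test within each status. SAP section 4 opens by allowing for exceptions and then says: "separate summary tables will be presented for the Completed and the Discontinued analysis sets with the following distinction". The Protocol Summary (section 3) agrees: "effectiveness and safety data will be presented separately based upon subject study status of Completed or Discontinued".
- **Sets.** Protocol 12.2 and SAP section 2 define Enrolled Dispensed as those exposed to study lenses. Completed and Discontinued are its two parts. No readable passage assigns a VA summary to the whole set.
- **Missing data.** Protocol 12.5: "No imputation for missing values will be carried out". The same section tabulates how many discontinue, and why, by lens group.
- **Collection.** The row "VA w/ study lenses (OD, OS Snellen distance" in SAP Table 10-1 (also Protocol Table 3-1) is ticked at Visits 1 to 6 and at Early Exit.
- **Numbers.** The Protocol Summary assigns about 80 subjects to test and 40 to control. SAP Table 1-1: "Target to complete: 90 subjects (60:30; Test:Control".

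**The concern.** Randomisation makes the two lens groups comparable at dispensing. Completion is settled later and can depend on how well the wearer sees with the assigned lens. Protocol 10.5.2 lets subjects leave at any time for any reason, and Protocol 11.1 lists lack of performance among the example device deficiencies. If more poor-seeing wearers leave one group, the Completed comparison flatters that lens. The Discontinued comparison is likewise between two self-selected groups.

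The split has two effects of its own. VA at Week 1, Week 2, Month 1 and Month 2 is observed in wearers who later leave, if they attended, yet it is tabulated apart from that of completers. Early Exit VA, the last reading in those who leave, is also kept apart. At stake is whether the description of VA, the only effectiveness evidence offered for the primary endpoint, refers to the wearers assigned to each lens or to those who stayed with it.

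**Working it through.** **1. The plan's numbers.** There is no powered sample size to reproduce: the readable text gives no SD, effect, margin or power. The counts agree with one another: 8 sites x 15 = 120; 120 split 2:1 = 80:40; 90 split 2:1 = 60:30.

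**2. Allowance for loss.** 1 - 90/120 = 1 - 60/80 = 1 - 30/40 = 25%, or 20 test and 10 control wearers. The Protocol glossary counts anyone who signs consent as enrolled, so the 120 may include screen failures. With an assumed screen-failure share s, loss after dispensing is 1 - 90/[120(1 - s)]:

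| s (assumed) | Dispensed | Loss after dispensing |
|---|---|---|
| 0% | 120 | 25% |
| 5% | 114 | 21.1% |
| 10% | 108 | 16.7% |
| 15% | 102 | 11.8% |
| 20% | 96 | 6.2% |

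The 80 and 40 assigned in the Protocol Summary support the first row; the glossary definition allows the others.

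**3. Where the split matters, visit by visit.**
- Week 1 to Month 2: later discontinuers who attended have values. A pooled table would include them; the split tables condition on later completion.
- Month 3: those who left normally have no value and nothing is imputed. The row is essentially completers-only with or without the split.
- Early Exit: the reading exists and appears by lens in the Discontinued tables only. It joins completers' VA only if a last-VA summary is defined.

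**4. Size under dropout that depends on VA.** All inputs here are assumptions. VA is normal in each group with SD 0.08-0.12 logMAR. The true difference D is 0.02-0.10, with test worse. The chance of leaving is 1/(1 + exp(-(a + b x VA))), with b = ln(OR)/0.1, so that OR is per line (0.1 logMAR). The intercept a is set so that (2 x test dropout + control dropout)/3 = 25%. The completers' difference is the difference in mean VA among those who stay.

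Example with SD 0.10 and D = 0.05:

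| OR per line | Dropout test / control | Completers' difference | Shortfall |
|---|---|---|---|
| 1.5 | 26% / 23% | 0.0486 | 3% |
| 2 | 27% / 21% | 0.046 | 7% |
| 3 | 28% / 20% | 0.043 | 14% |

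Over the whole grid the shortfall is 2-4% (OR 1.5), 5-10% (OR 2) and 10-18% (OR 3). The largest absolute shortfall is about 0.017 logMAR, at SD 0.12, D = 0.10 and OR 3. With 16.7% dropout the largest is about 0.013.

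**5. What pooling would change.** For last VA, an arm's mean among all dispensed exceeds its completers' mean by d x g, where d is the share leaving and g is how much worse leavers see than completers. The test-control difference therefore moves by dT x gT - dC x gC. With assumed values:
- 25% loss and a gap of 0.10 in both arms: 0.025 - 0.025 = 0.
- 30% and 15% loss, gap of 0.10 in both: 0.030 - 0.015 = 0.015.
- 25% loss, gap of 0.10 in the test arm only: 0.025.

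So 0.017 is the maximum over the grid in step 4, not a general bound. A larger shift needs leavers to see worse mainly in one arm.

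**The case against.** **A pooled table may exist.** Redactions fall inside Protocol 12.4 and 12.4.1.2 and SAP 4 and 4.3.1, and the SAP rule allows for exceptions. This stands: the point can be made only about the readable text, and the plan cannot be said to lack such a table.

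**The split does not cause the Month 3 gap.** A reader might infer that it makes Month 3 VA a completers' comparison. The documents do not support that. Dropout without imputation does it, and a pooled by-visit table would leave that row unchanged.

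**Nothing is discarded.** A reader might infer that Early Exit VA goes unused. It is tabulated by lens in the Discontinued tables, and the two sets together make up Enrolled Dispensed. If means and numbers are reported, a reader could combine them. Reasons for leaving and device deficiency categories are tabulated too, so loss driven by vision would leave a trace. This narrows the point, but the combined comparison would still be left to the reader.

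**25% is not a stated dropout rate.** It is inferred from a completion target and is the upper end.

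**The bias is small in absolute terms.** A reader might picture a subgroup of test wearers who fail on vision and all leave, so that the Completed tables lose the whole difference. That result follows from the assumption itself, and those wearers would appear under Discontinued Test. In the graded model the maximum is about one sixth of a line. This stands.

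**Conclusion.** The point holds in a limited form. The readable rule compares VA by lens only within groups defined by an outcome after randomisation, while the stated objective compares the lenses as assigned. What the split itself does is condition Week 1 to Month 2 VA on later completion and keep Early Exit VA apart from completers' VA.

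The resulting shortfall is 2-18% of the true difference under the assumed SD, difference and odds ratios, and it reaches 10% or more only when dropout depends strongly on VA. None of these inputs comes from the documents. There is no hypothesis test, so no error rate or power is involved; the harm is a possibly biased description. Severity is low to moderate: a cheap improvement that should be made, not a defect that undermines the trial.

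**What to change.** In Protocol 12.4 and SAP 4 and 4.3.1, first confirm whether a redacted passage already gives a by-lens VA summary for Enrolled Dispensed. If it does, the point is closed. If not, add one by randomised lens, showing:

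1. observed VA at each visit; and
2. last VA with study lenses, defined as Month 3 VA or, for subjects who left early, Early Exit VA.

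Give the logMAR statistics and the number of subjects and eyes contributing. Keep the Completed and Discontinued tables as supportive. Item 1 mends the visits before Month 3; only item 2 brings early leavers into an end-of-study figure.

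The cost is wording and one or two tables, with no extra visits or subjects. The last-VA summary mixes lengths of exposure, which should be stated beside it, and it may look slightly worse than the completers' figures.
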